4.2.2 Rationale for Dose Selection/Regimen/Modification

An open-label Phase I trial (Protocol 001) was conducted to evaluate the safety and clinical activity of single agent MK-3475. The dose escalation portion of this trial evaluated three dose levels, 1 mg/kg, 3 mg/kg, and 10 mg/kg, administered every 2 weeks (Q2W) in subjects with advanced solid tumors. All three dose levels were well tolerated and no dose-limiting toxicities were observed. This first in human study of MK-3475 showed evidence of target engagement and objective evidence of tumor size reduction at all dose levels (1 mg/kg, 3 mg/kg and 10 mg/kg Q2W). No MTD has been identified to date. Recent data from other clinical studies within the MK-3475 program has shown that a lower dose of MK-3475 and a less frequent schedule may be sufficient for target engagement and clinical activity.

PK data analysis of MK-3475 administered Q2W and Q3W showed slow systemic clearance, limited volume of distribution, and a long half-life (refer to IB). Pharmacodynamic data (IL-2 release assay) suggested that peripheral target engagement is durable (>21 days). A population pharmacokinetic analysis has been performed using serum concentration time data from 476 patients. Within the resulting population PK model, clearance and volume parameters of MK-3475 were found to be dependent on body weight. The relationship between clearance and body weight, with an allometric exponent of 0.59, is within the range observed for other antibodies and would support both body weight normalized dosing or a fixed dose across all body weights. MK-3475 has been found to have a wide therapeutic range based on the melanoma indication. The differences in exposure for a 200 mg fixed dose regimen relative to a 2 mg/kg Q3W body weight based regimen are anticipated to remain well within the established exposure margins of 0.5 – 5.0 for MK-3475 in the melanoma indication. The exposure margins are based on the notion of similar efficacy and safety in melanoma at 10 mg/kg Q3W vs. the proposed dose regimen of 2 mg/kg Q3W (i.e. 5-fold higher dose and exposure). The population PK evaluation revealed that there was no significant impact of tumor burden on exposure. In addition, exposure was similar between the NSCLC and melanoma indications. Therefore, there are no anticipated changes in exposure between different indication settings.

The rationale for further exploration of 2 mg/kg and comparable doses of pembrolizumab in solid tumors is based on: 1) similar efficacy and safety of pembrolizumab when dosed at either 2 mg/kg or 10 mg/kg Q3W in melanoma patients, 2) the flat exposure-response relationships of pembrolizumab for both efficacy and safety in the dose ranges of 2 mg/kg Q3W to 10 mg/kg Q3W, 3) the lack of effect of tumor burden or indication on distribution behavior of pembrolizumab (as assessed by the population PK model) and 4) the assumption that the dynamics of pembrolizumab target engagement will not vary meaningfully with tumor type.

The choice of the 200 mg Q3W as an appropriate dose for the switch to fixed dosing is based on simulations performed using the population PK model of pembrolizumab showing that the fixed dose of 200 mg every 3 weeks will provide exposures that 1) are optimally consistent with those obtained with the 2 mg/kg dose every 3 weeks, 2) will maintain individual patient exposures in the exposure range established in melanoma as associated with maximal efficacy response and 3) will maintain individual patients exposure in the exposure range established in melanoma that are well tolerated and safe.

A fixed dose regimen will simplify the dosing regimen to be more convenient for physicians and to reduce potential for dosing errors. A fixed dosing scheme will also reduce complexity in the logistical chain at treatment facilities and reduce wastage.

Recent in vitro studies have demonstrated enhanced radiosensitization with the administration of Pembrolizumab prior to the initiation of radiotherapy (Personal communication: [name]). As such, the initial dose of Pembrolizumab will be given in this study the week prior to the beginning of IMRT. This is consistent with other trials investigating the combination of PD-1 inhibitors and RT being done in the cooperative group setting. A pilot study that investigated the safety of adding Pembrolizumab to head and neck IMRT in addition to weekly cisplatin was recently presented at ASCO 2017. Powell, et al reported excellent safety profile of 27 patients with locally advanced head and neck cancer treated with chemoradiation with weekly cisplatin, and 70Gy in 35 fractions of IMRT along with Pembrolizumab 200mg fixed dose IV every 3 weeks beginning 4-7 days prior to the initiation of radiation 2 doses concomitant with IMRT and 5 additional doses post IMRT. 21 patients (78%) completed all planned doses of Pembrolizumab. 3 discontinued due to irAEs (G2 peripheral motor neuropathy, G3 AST elevation, G1 Lhermitte-like syndrome). 3 discontinued due to protocol reasons (early neck dissection -2 pts, prolonged hospitalization-1 pt). All pts completed the full radiation dose (70 Gy) without significant delay (defined as > 5 days). 23 (85%) received the goal target dose of cisplatin (≥ 200 mg/m²). There was one patient death due to concurrent illness, unrelated to treatment.¹⁸ Based on these results, the NRG Oncology HN-003 study which was designed as a phase I safety study of the addition of Pembrolizumab to postoperative head and neck IMRT and weekly cisplatin discontinued their planned phase I safety study and converted to an open label efficacy signal study. We therefore feel quite confident in the safety of our proposed regimen as our study involves less extensive IMRT fields and does not include any concurrent chemotherapy. We will however monitor DLTs very carefully and include that as a co-primary endpoint of the study.

4.2.3 Rationale for Endpoints

4.2.3.1 Efficacy Endpoints

1yr PFS in this patient cohort is suboptimal, and an important measure of disease control.

4.2.3.2 Safety Endpoints

The primary safety endpoints for this study will be dose limiting toxicity (DLT). DLT for this study is defined as the occurrence of a severe adverse event (AE) listed below that is *at least possibly*

related to pembrolizumab, and occurs from the initiation of treatment thru 30 days after the final administration of the study treatment. AEs will be graded according to NCI CTCAE version 4.0. At the completion of the study, a total DLT rate will be assessed. A DLT rate of $\leq 24\%$ will be deemed acceptable and if met, the regimen will be deemed appropriate for future study in randomized studies.

The following events will be considered a DLT:

- Any \geq Grade 3 immune-related toxicity (including graft rejection), except:
 - Grade 3 dermatologic toxicity resolving to Grade 1 or lower with < 2 weeks of systemic immunosuppression
- Any \geq Grade 3 non hematologic toxicity **except**:
 - Grade 3 in-field radiation dermatitis for which IMRT is not held or held ≤ 1 week (5 fractions)
 - Grade 3 mucositis for which IMRT is not held or is held ≤ 1 week (5 fractions)
 - Asymptomatic Grade 3-4 hypomagnesemia or hypokalemia
 - Grade 3 fatigue
 - Grade 3 dysphagia or feeding tube use
 - Grade 3 weight loss
 - Grade 3 pain
- Grade 3 neutropenia with fever (oral temperature $> 39^{\circ}\text{C}$)
- Grade 3 thrombocytopenia with bleeding
- Grade 4 neutropenia with/without fever, requiring antibiotics
- Grade 4 thrombocytopenia
- Toxicity of any grade that results in inability to complete IMRT within 8 weeks

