5.8.8 Radiation Therapy Treatment Interruptions

Treatment interruptions are strongly discouraged. Treatment breaks must be clearly indicated in the treatment record when they occur. Patients who have treatment interruptions in radiation for >3 weeks will be taken off study. The interruption of radiation therapy for grade 4 mucositis / dermatitis / dysphagia is at the discretion of the treating radiation oncologist. Treatment breaks, if necessary, ideally should not exceed five treatment days at a time and ten treatment days total. Treatment breaks should be allowed only for resolution of severe acute toxicity and/or for intercurrent illness and not for social or logistical reasons. Pembrolizumab will not be administered during radiotherapy treatment breaks.

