	
observation. (Note: Hospitalization [including hospitalization for an elective procedure] for a preexisting condition which has not worsened does not constitute a serious adverse event.); or
 
†Is a congenital anomaly/birth defect (in offspring of subject taking the product regardless of time to diagnosis);or
 
Is a new cancer; (that is not a condition of the study) or
 
Is an overdose (whether accidental or intentional). Any adverse event associated with an overdose is considered a serious adverse event. An overdose that is not associated with an adverse event is considered a non-serious event of clinical interest and must be reported within 24 hours.
 
Other important medical events that may not result in death, not be life threatening, or not require hospitalization may be considered a serious adverse event when, based upon appropriate medical judgment, the event may jeopardize the subject and may require medical or surgical intervention to prevent one of the outcomes listed previously (designated above by a †).

Duration	Record the start and stop dates of the adverse event. If less than 1 day, indicate the appropriate length of time and units
Action taken	Did the adverse event cause the Merck product to be discontinued?
Relationship to test drug	Did the Merck product cause the adverse event? The determination of the likelihood that the Merck product caused the adverse event will be provided by an investigator who is a qualified physician. The investigator's signed/dated initials on the source document or worksheet that supports the causality noted on the AE form, ensures that a medically qualified assessment of causality was done. This initialed document must be retained for the required regulatory time frame. The criteria below are intended as reference guidelines to assist the investigator in assessing

	
the likelihood of a relationship between the test drug and the adverse event based upon the available information.
 
The following components are to be used to assess the relationship between the Merck product and the AE;
 
the greater the correlation with the components and their respective elements (in number and/or intensity), the more likely the Merck product caused the adverse event (AE):

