The assessment of relationship will be reported on the case report forms /worksheets by an investigator who is a qualified physician according to his/her best clinical judgment, including consideration of the above elements.	

Record one of the following	Use the following scale of criteria as guidance (not all criteria must be present to be indicative of a Merck product relationship).
Yes, there is a reasonable possibility of Merck product relationship.	There is evidence of exposure to the Merck product. The temporal sequence of the AE onset relative to the administration of the Merck product is reasonable. The AE is more likely explained by the Merck product than by another cause.
No, there is not a reasonable possibility of Merck product relationship	Subject did not receive the Merck product OR temporal sequence of the AE onset relative to administration of the Merck product is not reasonable OR there is another obvious cause of the AE. (Also entered for a subject with overdose without an associated AE.)

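### Does a Yes/No causality entry undercount DLTs that radiotherapy could also explain?

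*Combined protocol and SAP*

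**What the plan says.** Section 4.2.3.2 fixes the attribution threshold for the primary safety endpoint: "DLT for this study is defined as the occurrence of a severe adverse event (AE) listed below that is *at least possibly" related to pembrolizumab. It then lists the qualifying events. Most Grade 3 radiation effects are exempt. Three kinds that overlap with radiation stay in: Grade 3 in-field dermatitis or mucositis when IMRT is held for more than one week, Grade 4 non-hematologic events, and toxicity of any grade that prevents completion of IMRT within 8 weeks. Section 5.8.8 foresees the Grade 4 kind: "The interruption of radiation therapy for grade 4 mucositis / dermatitis / dysphagia is at the discretion of the treating radiation oncologist".

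Table 6 in section 7.2.4 holds the only causality scale in the document. It has two entries. The affirmative one reads "Yes, there is a reasonable possibility of Merck product relationship", and its guidance includes "The AE is more likely explained by the Merck product than by another cause". The guidance for the negative entry is a list of alternatives, one of which is "there is another obvious cause of the AE". On the status of the guidance the table says "The criteria below are intended as reference guidelines to assist the investigator in assessing" the likelihood of a relationship, and it adds that not every criterion has to be met for a relationship to be indicated. On who decides: "The assessment of relationship will be reported on the case report forms /worksheets by an investigator who is a qualified physician", using clinical judgment.

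Section 8.2 gives the decision rule for 34 evaluable patients: 11 or more with DLT is too toxic, 8 or fewer is safe to proceed, and 9 or 10 leads to a review by the principal investigator.

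**The concern.** The two sections use different words for attribution, and no sentence links them. An event that pembrolizumab might have caused, but that radiation more probably caused, clears the bar in section 4.2.3.2. Under the Table 6 guidance it could be entered as No, because the drug is not the likelier explanation and radiation is an evident one. IMRT runs in weeks 2 to 7 alongside pembrolizumab in every patient, so such events can be expected.

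Any loss would go one way, toward declaring the regimen safe. It would also fall on the toxicity that the combination might plausibly worsen: section 4.2.2 gives radiosensitization as the reason for dosing pembrolizumab before radiotherapy. The rule has little slack, since recoding 3 of 11 DLT patients takes the result from too toxic (11) to safe (8).

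**Working it through.** **The plan's own figure.** Inputs from section 8.2: n = 34, acceptable rate 0.20, unacceptable rate 0.40, too toxic at 11 or more. With X ~ Binomial(34, p):

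- P(X ≥ 11 | p = 0.20) = 0.0620, against 6% stated.
- P(X ≥ 11 | p = 0.40) = 0.8617, against 86% stated.

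Both reproduce.

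**Effect of lost attributions.** Let m be the share of true DLT patients whose event is recorded as unrelated. The documents give no value, so m is an assumption. It is a share of patients: someone with a second qualifying event still counts. Replace p by 0.40 × (1 − m):

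| m (assumed) | p recorded | P(X ≥ 11) | P(X = 9 or 10) | P(X ≤ 8) |
|---|---|---|---|---|
| 0% | 0.40 | 0.862 | 0.104 | 0.034 |
| 5% | 0.38 | 0.802 | 0.142 | 0.056 |
| 10% | 0.36 | 0.729 | 0.183 | 0.088 |

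In patients, a true rate of 40% means 34 × 0.40 = 13.6 expected DLTs, so these losses are 0.68 and 1.36 patients. More than half of the probability that leaves the too-toxic zone goes to the review zone, not to safe: 0.0374 of 0.0592 at 5%, and 0.0787 of 0.1326 at 10%.

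**Are larger losses plausible?** The only related data are the pilot in section 4.2.2, with 27 patients on 70 Gy plus cisplatin and pembrolizumab: "All pts completed the full radiation dose (70 Gy) without significant delay (defined as > 5 days"). That is 0 of 27. The exact 95% upper limit is 1 − 0.025^(1/27) = 0.128. A 25% loss would need 0.40 × 0.25 = 10 points of misattributed DLTs. If all of these came from delays, 0 of 27 would have probability 0.90^27 = 0.058. Losses of 5% and 10% need 2 and 4 points, with 0.98^27 = 0.58 and 0.96^27 = 0.33. The pilot therefore sits easily with the table's rows and poorly with much larger losses. It used a different regimen and says nothing about Grade 4 events without a delay.

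**The passages side by side.**

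1. What the investigator records is the label. An event possibly due to pembrolizumab fits the label of a reasonable possibility and does not fit its negation. To reach No, one must set the guidance above the label that it explains.
2. The requirement that the drug be the likelier cause is one guidance criterion, and the table says that not all need to be met.
3. Neither section 4.2.3.2 nor section 8 says that DLT status is computed from the Table 6 entry. Section 4.2.3.2 states its own threshold and, as the specific definition of the endpoint, governs.
4. That definition retains dermatitis and mucositis with a long IMRT hold, and failure to complete IMRT in time. Radiation is an evident contributor to nearly all of these. If that alone made an event unrelated, the items would be almost empty, so that cannot be the intended reading.
5. Events marked No are not lost. Section 7.2 records adverse events whether or not they are related, section 8.3 tabulates them by category and grade, and section 5.8.8 requires treatment breaks to be documented.

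**The case for a change.** The strongest case for a change is that this is a primary endpoint in an open-label trial, that section 8 describes no independent DLT adjudication, and that the label and the guidance in Table 6 pull in different directions. Two conscientious investigators could classify the same Grade 4 mucositis differently, and the error would favour the regimen. A separate attribution field with a possible level, plus a count of all listed events regardless of cause, would cost little.

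Part of this stands. The mapping is nowhere written down, and the stricter reading is available to someone who takes the guidance literally. But the text permits that reading and does not compel it. Disagreement between investigators is a feature of any causality judgment, including one on a five-level scale.

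The remedies gain little. A second attribution field for the same event invites discordant entries, and it presumes that the forms, which are not in the document, lack such an item. An all-cause count changes no decision rule and can be made from data already collected. It could not replace the primary count: if related DLTs run at 20% and unrelated events add an assumed 5 or 10 points, P(X ≥ 11) rises from 0.062 to 0.211 (p = 0.25) or 0.446 (p = 0.30), condemning an acceptable regimen too often.

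**Conclusion.** No change to the plan. The gap is a missing cross-reference between two nearly equivalent phrases, and anyone applying section 4.2.3.2 as written will fill it sensibly: a listed event with a reasonable possibility of relation to pembrolizumab is a DLT, whether or not IMRT also contributed. Counted that way, the design keeps its 6% and 86%.

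The exposure is confined to the few radiation-overlap events that are not exempt; immune-related and hematologic DLTs are little affected. The size of any undercount cannot be derived from the documents. An assumed loss of 5% to 10% of DLT patients at a true rate of 40% costs 6 to 13 points of power and adds 2 to 5 points to the chance of a safe verdict. This rests on two readings: that the endpoint definition governs over general reporting guidance, and that the recorded label, not the explanatory line beneath it, carries the meaning of the entry. Both are the natural ones.

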2.0 TRIAL DESIGN

2.1 Trial Design

- This is a phase II trial evaluating the addition of concurrent and adjuvant fixed-dose pembrolizumab in combination with standard IMRT, in order to establish safety and estimate efficacy of this regimen to be tested in a subsequent randomized registration trial. Thirty seven patients will be enrolled.
- The primary safety endpoint will be proportion of DLTs. The primary efficacy endpoint will be 1-year PFS. The primary signal to move forward with a subsequent confirmatory randomized study will be a $\leq 24\%$ overall DLT rate and a favorable 1yr PFS estimate compared to historical controls.

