8.0 STATISTICAL ANALYSIS PLAN

8.1 Study Design

This is a phase II trial evaluating the addition of concurrent and adjuvant fixed-dose pembrolizumab in combination with standard IMRT, in order to establish safety and estimate efficacy of this regimen to be tested in a subsequent randomized registration trial. At the conclusion of the study, the primary safety endpoint will be proportion of DLT. The primary efficacy endpoint will be 1-year PFS. Progression-free survival (PFS) will be calculated from treatment initiation to disease progression or death from any cause or last follow up.

8.2 Justification of Design and Sample Size:

The target sample size will be 34 patients. Assuming a <10% drop out or ineligibility rate, 37 patients will be enrolled to ensure 34 evaluable patients (all evaluable patients will be analyzed). The sample size was generated based on the primary safety endpoint. DLT $\leq 20\%$ is acceptable and $\geq 40\%$ is unacceptable. If 11 or more of 34 patients experience DLT, this regimen will be considered too toxic. The significance level and power of this design are 6% and 86%, respectively. If 8 or fewer patients experience DLTs, the regimen will be deemed safe to proceed for further study. If 9 or 10 patients experience DLTs, the PI will examine the type, reversibility and duration of DLTs and a careful decision will be made whether to pursue this regimen further in this adjuvant population.

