8.3 Statistical Analysis Plan

DLT will be estimated using an exact 95% confidence interval. If 11 or more patients experience DLT the regimen will be considered too toxic. One-year PFS will be estimated using the Kaplan-Meier method and a 95% confidence interval constructed using Greenwood's method. One year PFS outcomes will be assessed overall and also separately for immunocompetent patients vs. immunosuppressed patients (e.g. CLL). These outcomes will be compared to our historical dataset for both subsets respectively. Adverse events will be tabulated by category and grade. The rates of

adverse events will be estimated using an exact 95% confidence. The relationship between 1yr PFS and baseline PD-L1 expression will be assessed using logistic regression. Immunoprofiles in peripheral blood in serial samples will be tested using random effects ANOVA. Bioinformatic analysis will be applied to all genomic and transcriptomic data.

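### The plan's too-toxic count of 11 DLTs is a final verdict, but nothing in the documents ties it to accrual

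*Combined protocol and SAP*

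**What the plan says.** Two sections place the DLT assessment at the end of the trial: 4.2.3.2 ("At the completion of the study, a total DLT rate will be assessed") and 8.1 ("At the conclusion of the study, the primary safety endpoint will be proportion of DLT").

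Section 8.2 gives the decision count: "If 11 or more of 34 patients experience DLT, this regimen will be considered too toxic". Section 8.3 repeats it without a denominator: "If 11 or more patients experience DLT the regimen will be considered too toxic". Neither says when the count is looked at or what then happens to enrolment. Section 8.2 also states that "37 patients will be enrolled to ensure 34 evaluable patients (all evaluable patients will be analyzed"), so the number analysed may lie between 34 and 37. It gives a significance level of 6% and power of 86%, with 20% as the acceptable and 40% as the unacceptable DLT rate.

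Under 2.1, the signal to go on to a randomized study needs both an acceptable "overall DLT rate and a favorable 1yr PFS estimate compared to historical controls". The acceptable rate is at most 24% in 2.1 and 4.2.3.2, and at most 20% in 5.4.

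Oversight is described in four places. Section 5.10 item 3 lists the incidence or severity of adverse drug reactions among the criteria that lead to early termination. Section 4.2.2 promises careful DLT monitoring. Section 7.2.6 sends all serious adverse events to the Data Safety Toxicity Committee. Section 10.6 commits the trial to the institutional Data and Safety Monitoring Plan. None of these gives a DLT count.

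**The concern.** The count of 11 is a verdict that later patients cannot reverse. If it is reached before enrolment ends, the plan as written lets enrolment continue to its target. Because 2.1 requires both conditions, a good PFS result cannot rescue a regimen that has failed on DLTs. Resected patients would then be exposed without any effect on the safety decision.

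The reporting route adds to this. The committee in 7.2.6 receives SAEs, but some DLTs need not be SAEs. One listed DLT is "Toxicity of any grade that results in inability to complete IMRT within 8 weeks". Another possible case is an isolated Grade 3 AST elevation without hospitalization; 4.2.2 reports a Grade 3 AST elevation from the pilot study. Without raised bilirubin it also falls outside the hepatic event of clinical interest in 7.2.3.2. The committee may therefore not see every DLT. How many would be missed is not known.

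**Working it through.** **Inputs from the documents.** Evaluable target 34, enrolment 37, too-toxic count 11, DLT rates 20% and 40% (8.2). The DLT window "occurs from the initiation of treatment thru 30 days after the final administration of the study treatment" (4.2.3.2). Doses fall in weeks 1, 4, 7, 10, 13 and 16 (Table 2), so the last dose is on day 5 × 21 = 105 and the window closes on day 105 + 30 = 135.

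**Assumptions.** The documents give neither an accrual rate nor the timing of DLTs. I assume Poisson accrual of 1 to 6 patients per month and DLT onset uniform over the 135 days.

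**1. The plan's own figures.** P(X ≥ 11) for X ~ Binomial(34, p) is 0.0620 at p = 0.20 and 0.8617 at p = 0.40. The stated 6% and 86% are reproduced as a single end-of-study test on 34 patients.

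**2. The same count at other numbers evaluable.**

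| Evaluable | Alpha (20%) | Power (40%) |
|---|---|---|
| 34 | 6.2% | 86.2% |
| 35 | 7.5% | 88.8% |
| 36 | 8.9% | 91.0% |
| 37 | 10.5% | 92.8% |

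**3. The verdict is final.** With 11 DLTs among evaluable patients, the final rate is at least 11/37 = 29.7%, above both 24% and 20%. The count cannot fall, provided that patients are not reclassified as non-evaluable afterwards.

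**4. Closing accrual at the 11th DLT, no lag.** Let T be the evaluable patient in whom the 11th DLT occurs. Then P(T = t) = C(t−1, 10) p^11 (1−p)^(t−11), and mean enrolment is E[min(T, 34)].
- At 40%: P(T ≤ 34) = 0.8617 and the mean of T given that is 25.69, so 0.8617 × 25.69 + 0.1383 × 34 = 26.8. The 11th DLT falls by patient 25 with probability 0.41 and by patient 30 with probability 0.71.
- At 20%: 0.0620 × 30.47 + 0.9380 × 34 = 33.8.

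The trial crosses 11 within n patients exactly when the fixed-sample count would, so alpha and power at a given n are unchanged.

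**5. With lag.** Simulation of 100,000 trials, cap of 34 evaluable, true rate 40%, mean number of patients spared:

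| Accrual per month (assumed) | DLT known at onset | DLT known at next scheduled AE visit |
|---|---|---|
| 1 | 5.4 | 5.2 |
| 2 | 3.9 | 3.4 |
| 3 | 2.7 | 2.1 |
| 4 | 1.7 | 1.2 |
| 6 | 0.6 | 0.3 |

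Visit detection uses days 0, 21, 42, 63, 84, 105 and 135. At a true 30%, 0.5 to 1.6 patients are spared at 1 to 3 per month. At a true 20%, mean enrolment stays at 33.8 of 34 or more.

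**6. Cost in precision.** The 95% half-width for 1-year PFS, assuming complete follow-up, is 1.96 √(s(1−s)/n). For an assumed s of 60%, 70% and 80% it is 16.5, 15.4 and 13.4 points at n = 34, and 18.5, 17.3 and 15.1 points at n = 26.8. That is about 2 points wider.

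**The case against.** The strongest reply is that a single-stage design with an end-of-study verdict is coherent, and that protection already exists. Section 5.10 makes adverse reaction incidence or severity a ground on which the trial will end, not merely one on which it may. Because 8.3 attaches no timing to the count of 11, it can be read as feeding that criterion as soon as it is reached. The institutional plan may also hold an explicit rule. This stands as far as it goes: what is missing is an explicit link, and the documents cannot show whether patients would in practice be unprotected.

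The benefit is also modest and rests on assumed inputs. At 4 to 6 patients per month few are spared. Some DLTs cannot be settled at onset: Grade 3 dermatologic toxicity depends on how it resolves, dermatitis and mucositis on how long IMRT is held, and one item on whether IMRT is finished in 8 weeks. Adjudication would delay the tally further, and the simulations do not include that delay. This stands too.

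Two stronger readings are tempting, and the documents support neither. A reader might infer that the trial has no means of stopping for toxicity; 5.10, 4.2.2, 7.2.6 and 10.6 say otherwise. A reader might also infer that the stated 6% and 86% are wrong; they are correct for 11 of 34, and the text only omits that they do not carry over to 35 to 37 evaluable patients.

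**Conclusion.** The point holds as a gap in explicitness with a cheap remedy. The DLT rate is assessed at study end, the count of 11 is not tied to accrual, and no supplied section names a DLT count that triggers action.

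At a true DLT rate of 40%, the most that closing accrual could save is 34 − 26.8 = 7.2 evaluable patients on average, and that requires instant knowledge of each DLT. Under the lag assumptions the saving is 5.4 down to 0.6 patients as accrual rises from 1 to 6 per month, and less with visit-based detection or adjudication. An acceptable regimen loses almost nothing. Confidence is medium, because the accrual rate, DLT timing and content of the institutional plan are unknown.

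**What to change.** - **5.10 and 8.2:** state that confirmed DLTs are tallied as they are established, at the latest at each scheduled AE visit, and that accrual closes when the tally among evaluable patients reaches the existing count of 11. If the institutional plan already has a DLT rule, cite it and reconcile it with 11.
- **7.2.6:** extend the route to the Data Safety Toxicity Committee to DLTs that are not SAEs.
- **4.2.3.2 and 8.1:** align the timing words with the running tally.
- **8.2:** define evaluability without regard to DLT outcome. Counting a patient as evaluable because a DLT occurred would bias the rate upward.
- **8.2 and 8.3:** state that 6% and 86% apply to 11 of 34, and give the figures for 35, 36 and 37 evaluable patients.

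No new threshold is needed, and the management of patients already on treatment is outside this point.

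The cost is short edits in six sections (4.2.3.2, 5.10, 7.2.6, 8.1, 8.2, 8.3), a running tally from AE data already collected (7.1.2.1, 7.2), and some adjudication effort. If accrual closes early, the PFS and DLT estimates rest on fewer patients, and the DLT estimate runs slightly high (mean 0.42 at a true 0.40 with no lag). That loss falls on a regimen that the plan already judges too toxic.
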